4.4 END-OF-STUDY DEFINITION

A participant is considered to have completed the study if she has completed Time 1 (baseline), Time 2 (6 months) and Time 3 (12 months) data collection.

5 STUDY POPULATION

5.1 INCLUSION CRITERIA

Inclusion criteria are: age 40-55 years; self-identify as Latina; understand spoken English or Spanish; perimenopausal based upon the Study of Women's Health study definitions [40]: menstrual bleeding in the past three months, but timing of periods have varied in past year, or no menstrual bleeding in the past 3-11 months; intact uterus and at least one ovary; not currently pregnant; no hormone therapy or oral contraceptives in the past three months (as these may alter bleeding patterns). These eligibility criteria are consistent with previous observational studies and clinical trials in perimenopausal women [41] and are standard to clearly assess menopausal status in midlife women.

5.2 EXCLUSION CRITERIA

Exclusion criteria are: history of CVD (heart attack, stroke, coronary heart disease), impaired physical mobility, or difficulty exercising. Women will not be excluded if on current anti-hypertensive, lipid-lowering, or diabetes medications.

5.3 LIFESTYLE CONSIDERATIONS

N/A

5.4 SCREEN FAILURES

Screen failures will not be consented or enrolled in the study. We will keep track of screen failures and reasons why they failed to meet inclusion criteria.

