1 PROTOCOL SUMMARY

1.1 SYNOPSIS

Title:	Reducing Cardiovascular Risk in Perimenopausal Latinas: Pilot Study of a Multi-Component Intervention
Grant Number:	1K23MD014767-01
Study Description:	
Cardiovascular disease (CVD) is the leading cause of death among Latinas, exceeding rates for Latino men. Evidence suggests that Latinas have a significantly worse CVD risk factor profile than non-Hispanic White women. Furthermore, Latinas are considerably less likely to meet physical activity and dietary guidelines than non-Hispanic White women, particularly during perimenopause. Prior studies have shown that increases in CVD risk can be prevented in perimenopausal women using a lifestyle dietary and physical activity intervention; however, these studies did not include Latinas. To address these deficits, the aim of this study is to pilot test a multi-component behavioral intervention among perimenopausal Latinas (age 40-55) that integrates evidence-based education with physical activity, stress management, and coping skills training to: 1) reduce biologic CVD risk, including adiposity, blood pressure and arterial stiffness; 2) improve nutrition, physical activity, and sleep; and 3) improve stress management, coping strategies, and self-efficacy.

Objectives*:	
Primary Objective: To examine the feasibility and initial efficacy of the multi-component behavioral intervention to reduce biologic CVD risk from Time 1 (baseline) to each of Time 2 (6 months) and Time 3 (12 months).
 
Secondary Objectives: To evaluate the initial efficacy of the intervention to improve secondary outcomes of health behaviors, adiposity, inflammatory and stress biomarkers, and vasomotor symptoms from Time 1 (baseline) to each of Time 2 (6 months) and Time 3 (12 months).

Endpoints*:	
Primary Endpoint:
 
a) Feasibility: enrollment and retention rates; barriers and facilitators to enrollment; intervention fidelity; suitability of study procedures and outcome measures; and participant satisfaction with the intervention and study protocol.b) Biologic CVD risk: blood pressure, arterial stiffness, lipids, blood glucose. 
Secondary Endpoints: a) Health behaviors: nutrition, physical activity, sleep, coping strategies.

b) Other biological factors: adiposity, inflammatory and stress biomarkers, vasomotor symptoms.

Study Population: A total of 80 perimenopausal Latinas.

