2 INTRODUCTION

2.1 STUDY RATIONALE

Background: CVD remains the leading cause of death for women globally. In women, risk of CVD increases substantially during perimenopause. Latinas have a significantly worse CVD risk factor profile than non-Hispanic White women, attributable to several factors including lower socioeconomic position, interpersonal violence, discrimination, and stress. These factors are related to CVD through their influence on health behaviors as well as potential mechanisms involving inflammatory and neuroendocrine pathways. Despite their increased risk, however, perimenopausal Latinas remain underrepresented in CVD research.

Methods: This study is guided by the National Institute of Minority Health and Health Disparities (NIMHD) Framework, which considers the interplay between sociocultural environment, built environment, behavioral influences, and biological influences on health. Using a cluster randomized two-group, repeated measures experimental design, the goal of this study is to investigate the feasibility and initial efficacy a 12-month intervention integrating evidence-based education and coping skills training with physical activity and stress management. The intervention has three phases: 12 weekly sessions (Phase I: education, physical activity, stress management, coping skills training) followed by 3 monthly sessions of continued support (Phase II); and finally 6 months of skill maintenance on their own (Phase III). Measurement visits will occur at baseline, 6, and 12 months. We will conduct in-depth exit interviews with participants to assess barriers and facilitators to recruitment and enrollment, delivery of the intervention, fidelity, and suitability of assessment procedures. We will partner with local churches and community centers in two counties to recruit participants and deliver the intervention. Data will be collected at Time 1 (0 months [baseline]) to Time 2 (6 months [completion of the intervention]) and Time 1 to Time 3 (12 months [after 6 months with no contact from the study staff]). Data collected will include blood pressure, lipid profile, blood glucose, and arterial stiffness. Secondary outcomes will include health behaviors and self-efficacy, adiposity, inflammatory and stress biomarkers, and vasomotor symptoms.

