Data will be collected at Time 1 (baseline [0 months]), Time 2 (post Intensive Intervention and Continued Support [6 months]), and Time 3 (6 months after completion of Continued Support [12 months]). Data collected will include the primary outcomes of blood pressure, arterial stiffness based on carotid-femoral pulse wave velocity measures, lipid profile (total cholesterol, high-density lipoprotein, low-density lipoprotein, triglycerides), blood glucose; secondary outcomes of health behaviors (Sleep Quality Questionnaire, Food Behavior Checklist, Physical Activity Questionnaire, and 7-day Accelerometer), self-efficacy (Eating Self-Efficacy Scale and Exercise Self-Efficacy Scale), body mass index, waist circumference, hs-CRP, hair cortisol, and vasomotor symptoms. We will also evaluate the feasibility of the study including, number of eligible participants; methods of identifying/recruiting participants; willingness of participants to be randomized; practicality of delivering the intervention in the proposed setting; enrollment and retention rates, and suitability of the intervention and assessment protocol. Data analysis will use descriptive statistics and general linear mixed models to test the hypotheses. Both intervention and control group participants will each receive \$120 for their time during data collection visits (\$35 at Time 1, \$40 at Time 2, \$45 at Time 3) and \$5 to help with transportation costs each time they come to class or data collection visit.

Participants in the intervention group will receive a 12-week Intensive Intervention (Phase I) with weekly 2-hour sessions consisting of 60 minutes of nutrition and exercise education and coping skills training, a 45-minute physical activity class, and 15-minute stress management session. During Continued Support (Phase II), participants will meet monthly for 3 months for 60 minutes of classroom discussion regarding problems they are having with nutrition and physical activity. Data collection in the wait-list control group will occur at the same time intervals as women in the intervention group. Following the last data collection, we will offer Phase I of the intervention to women in the wait-list control group.

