Subject Accrual and Compliance with Inclusion/Exclusion. All data from participants screened for the study will be entered into the REDCap electronic study database. Designated research staff will collect, gather, and enter required data (written informed consent, Health Insurance Portability and Accountability Act (HIPAA) authorization, medical history and demographics) onto study data forms. Screened patients who do not meet study eligibility will have specific screening data entered into the study database. The collected data will be helpful in examining the patient population and feasibility of enrollment criteria and will include gender, age, race and reason for exclusion. All dates will be shifted and other Personal Health Information (PHI) will be removed from the study database upon study completion.

Participant Compliance to the Intervention. Data on compliance to the intervention will be collected weekly by the senior RA and reviewed quarterly by the Co-Mentors, scientific advisors, the Senior RA, Safety Officer, and PI. Compliance on the part of participants will be evaluated by attendance and process evaluation as outlined in the study. If intervention attendance drops below 80%, participants who have stopped coming will be called to ask for feedback. Using information gained from these phone interviews, the PI will schedule a meeting with the Co-mentors, scientific advisors, and the Safety Officer to discuss methods for improving compliance.

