9 STATISTICAL CONSIDERATIONS

9.1 STATISTICAL HYPOTHESES

Aim 1: To examine the feasibility of the multi-component behavioral intervention. We will assess enrollment and retention rates; barriers and facilitators to enrollment; intervention fidelity; suitability of study procedures and outcome measures; and participant satisfaction with the intervention and study protocol.

Aim 2: To evaluate the initial efficacy of the intervention by comparing an intervention group to a wait-list control group (n=80; 40 per group) in a pilot study to a) decrease the primary outcomes of biologic CVD risk factors (blood pressure [BP], arterial stiffness, lipids, blood glucose); b) improve secondary outcomes (health behaviors: nutrition, physical activity, sleep, coping strategies) and other biological factors related to CVD risk (adiposity, inflammatory and stress biomarkers, vasomotor symptoms) from Time 1 (baseline) to Time 2 (6 months) and Time 3 (12 months).

Hypotheses and Statistical Considerations: This pilot study will descriptively assess the feasibility and validity of the cluster randomized controlled trial plan and is not expected to test the hypotheses of the main clinical trial.

We expect that on average, the intervention group will have a slower progression or a decrease in BP, arterial stiffness, lipids, and blood glucose compared to the wait-list control from Time 1 (baseline) to Time 2 (6 months) and Time 3 (12 months).

We expect the intervention group will show improvements in health behaviors (nutrition, physical activity, sleep, coping strategies, self-efficacy), adiposity, inflammatory and stress biomarkers, and vasomotor symptoms from Time 1 (baseline) to Time 2 (6 months) and Time 3 (12 months).

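### Barriers to enrollment is a primary feasibility endpoint, but the plan makes no provision for recording why eligible women decline

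*Combined protocol and SAP*

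**What the plan says.** The primary feasibility endpoint in the Synopsis (1.1) includes "enrollment and retention rates; barriers and facilitators to enrollment". Aim 1 in 9.1 repeats it: "We will assess enrollment and retention rates; barriers and facilitators to enrollment; intervention fidelity". Section 2.3.1 adds further feasibility measures, among them the number of eligible women and "willingness of participants to be randomized".

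The data sources named for these are:

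- **Enrollment barriers.** Section 2.1: "We will conduct in-depth exit interviews with participants to assess barriers and facilitators to recruitment and enrollment". The schedules in 1.3 and 8.1 place the exit interview at 12 months.
- **Screening reasons.** Section 5.4: "We will keep track of screen failures and reasons why they failed to meet inclusion criteria". The subject accrual paragraph of 8.3.3.2 agrees: "Screened patients who do not meet study eligibility will have specific screening data entered into the study database". The items it lists for these women are demographic ones and the reason for exclusion.
- **Phone screen.** Section 5.5 lists eligibility items only: age, menstrual and surgical history, hormone use and CVD history.
- **Analysis.** For Aim 1, 9.4.1 plans descriptive summaries of enrollment, retention and attendance, with fidelity and satisfaction. It mentions neither refusals nor reasons for refusing.

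**The concern.** An eligible woman can leave at two points before enrollment: after the phone screen, or at the baseline visit, where the requirements, risks and random assignment are explained (5.5). She is not a screen failure, so 5.4 does not call for a reason. She is not a participant at 12 months, so the exit interview does not reach her. Yet she is the woman for whom some barrier was decisive.

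The plan asks for reasons at most other exits: failing eligibility (5.4), missing sessions (6.2.1), ceasing to attend (5.5, 8.3.3.2) and withdrawing (7.2). The eligible woman who declines is the exception.

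At stake is what the pilot passes on to the larger trial, which 8.3.4 says this information is meant to inform. If acceptance is low, the remedy depends on whether women object to assignment by church, the 12-month wait, the weekly classes or the blood and hair sampling. Interviews with women who accepted all of these are a weak guide to that.

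**Working it through.** The documents state no figure on this point, so the main check traces each measure to its source and to the women that source covers.

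1. **Reasons for ineligibility.** Source: screening record (5.4, 8.3.3.2). Covers women who fail the criteria.
2. **Barriers to enrollment.** Source: exit interview (2.1; timing in 1.3 and 6.2.1). Covers women who enrolled and are still reachable at 12 months.
3. **Reasons eligible women decline.** No source is stated. Three places come close. The screening and enrollment logs (1.3, 8.1) have no described contents. Section 8.3.3.2 sends all screened women's data to REDCap but names no decline reason. The semi-annual qualitative reports (8.3.4) cover barriers to participation, using phone calls and end-of-study surveys, without saying whether non-participants are included.
4. **Willingness to be randomized.** No source or denominator is stated. Churches are randomized after enrollment and baseline (6.3), so every enrolled woman accepted random assignment when she consented.

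**Illustration of size.** Input from the documents: 80 women enrolled (1.1). Assumed input: acceptance rate *a* among eligible women, for which no figure is given. Decliners = 80/*a* − 80.

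- *a* = 80%: 80/0.80 = 100 eligible, 20 decline
- *a* = 70%: 80/0.70 ≈ 114 eligible, 34 decline
- *a* = 60%: 80/0.60 ≈ 133 eligible, 53 decline
- *a* = 40%: 80/0.40 = 200 eligible, 120 decline

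**Effect on willingness to be randomized.** Define it as eligible women who did not decline because of assignment, divided by all eligible women. Without decline reasons, the counts give only bounds. If every decliner objected to assignment, it is 80/(80/*a*) = *a*; if none did, it is 100%. At *a* = 60% the pilot could say only that willingness lies between 60% and 100%; at *a* = 40%, between 40% and 100%. Recorded reasons narrow that interval.

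**The case against.** The strongest reply is that the gap is inferred from silence and that other parts of the plan may cover it. Three stronger readings are tempting, and the documents do not support them.

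- **That eligible decliners are never asked.** The logs are a dedicated feasibility instrument with undescribed contents, and the phone calls in 8.3.4 are not attributed to any group. Either could hold decline reasons. What can be said is that no provision for it is documented.
- **That the pilot cannot tell narrow eligibility from an unattractive offer.** All screened women are entered in the database (8.3.3.2), the number eligible is a listed measure (2.3.1) and enrollment rates are summarized (9.4.1). Eligible/screened and enrolled/eligible can therefore be formed. Only the reasons for refusal would be missing.
- **That willingness to be randomized is 100% by construction.** This takes participants to mean enrolled women. Sections 2.3.1 and 8.3.3.2 also use the word for women before enrollment, and random assignment is explained while women can still decline (5.5). The denominator is undefined, not fixed. Withdrawals after the assignment is disclosed would have a reason recorded (7.2), though these may reflect a reaction to the group received as well as to being randomized.

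It is also fair to say that log fields are often left to a manual, and that 5.5 provides for advice from community leaders. That advice is sought only if enrollment proves difficult and is not data from the women who declined. A primary feasibility endpoint should have a stated source that reaches the women concerned.

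**Conclusion.** The point holds in a limited form. Followed as written, the plan would answer the enrollment-barriers endpoint mainly from women whom no barrier stopped, and it documents no way of learning why eligible women refuse. Screening and enrollment counts may still show whether eligibility or acceptance is limiting. Willingness to be randomized needs a defined denominator; measured only in enrolled women at consent, it carries no information.

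The 20 to 120 unexplained decliners rest wholly on an assumed acceptance rate of 80% down to 40%, and on the logs holding no decline reason. They show scale and are not estimates. The conclusion does not depend on them.

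**What to change.** 1. In 5.4 and the subject accrual paragraph of 8.3.3.2, state that the screening and enrollment log records, for each eligible woman who declines, the stage (phone screen or baseline visit), the recruiting site and one voluntary coded main reason. Codes could be assignment by church or the 12-month wait, time, transport, blood or hair sampling, other, and no answer.
2. In 9.4.1, add to Aim 1 the proportions eligible/screened and enrolled/eligible and the distribution of decline reasons, by recruiting site.
3. Name this log, together with the exit interviews, as the source for barriers and facilitators to enrollment.
4. Define willingness to be randomized as eligible women not declining because of assignment, divided by all eligible women, and show how many gave no reason.

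If the log already records decline reasons, steps 1 and 3 need only a sentence saying so. The cost is one coded field in an existing log and about a minute of staff time per refusal. Some women will give no reason, which leaves residual uncertainty. The field should be in place before recruitment, because reasons cannot be reliably recovered later.

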5.5 STRATEGIES FOR RECRUITMENT AND RETENTION

Procedures for Minority Recruitment and Enrollment and Challenges

This study builds on established partnerships between UNC-CH, local churches, and community centers in Orange County and Durham County. [name] and [name] have extensive experience working with these communities in prior studies, and will guide my community engagement. To assure that we meet enrollment targets, all project staff will be bilingual (English, Spanish) and all study materials (recruitment, intervention, and instruments) will be available in Spanish. Participants will be recruited by a Community Health Worker (CHW) and Research Assistant (RA) from local churches, and community centers in Orange County and Durham County. Two months before enrollment, the Project Coordinator will meet with staff at the churches and community centers to confirm recruitment strategies and place Spanish language flyers with information about the study and eligibility criteria in the entrance and common areas. The flyers will contain a phone number for individuals to call if they're interested in participating in the study. Additionally, the CHW and RA will be available weekly after church services and monthly at events organized by community centers. RAs will record the names and

telephone numbers of interested women privately and schedule them for a phone screening. This approach worked well in prior studies that enrolled 56 women in over a month [42]. We plan to enroll 8-10 women per week and can extend the timeline for enrollment if needed. If we have difficulty enrolling participants we will ask community leaders from the recruitment sites for advice. The Project Coordinator will conduct a phone screening, asking women for their birthdate, last menstrual period, regularity of menstrual periods, history of hysterectomy or oophorectomy, use of hormone therapy or birth control pills, and history of CVD. Women who meet the study criteria will be scheduled for a baseline visit to confirm eligibility, review the study, requirements of participants, and the risks and benefits of participating, random assignment and answer questions. Data collection will occur in a private location in the participant's home (approximately 90 minutes). We have time in the schedule for make-up data collections.

Procedures for Minority Retention and Challenges

To strengthen retention, our intervention sessions will be interactive, with culturally-tailored content developed to engage and sustain participants' interest (*Su Corazón, Su Vida* curriculum and coping skill training). Women who miss a learning session will be offered an opportunity to review the weekly class content over the phone, and will be reminded when the next class will be held. We will provide women with handouts including tips, a list of resources, recipes, and illustrations in Spanish on how to improve their nutrition, physical activity, and sleep. We will ask participants for phone numbers of family members and permission to call them if we cannot contact them. We will be flexible in scheduling enrollment and data collection appointments and send thank you cards. We will remind participants of their data collection visits one week before and confirm the day before the appointment. Participants in both groups will receive \$35 after the baseline visit, \$40 after the 6-month visit, and \$45 after the 12-month data collection. These approaches have been successful in prior studies with Latinas, with <20% attrition [43]. We will make every effort to keep our attrition lower than 20%; if attrition exceeds 20%, we will contact the participants to ask why they stopped coming and develop strategies to assist them to continue in the study if they wish. We will also meet with our Community Advisory Board to develop and implement strategies to improve retention.

6 STUDY INTERVENTION(S) OR EXPERIMENTAL MANIPULATION(S)

6.1 STUDY INTERVENTION(S) OR EXPERIMENTAL MANIPULATION(S) ADMINISTRATION

6.1.1 STUDY INTERVENTION OR EXPERIMENTAL MANIPULATION DESCRIPTION

Intensive Intervention

The intensive intervention consists of 12 weekly bilingual (English, Spanish) sessions that include 60 minutes of interactive learning, 45 minutes of physical activity, and a 15-minute stress management session. The first 8 sessions will integrate education from SCSV related to CVD risk awareness, healthy food choices, physical activity, blood pressure control, and diabetes. To enhance the relevance of the curriculum to perimenopause, we will include messages from American Heart Association Go Red Por Tu Corazón. Each week CHWs will give participants a SCSV or AHA Go Red Por Tu Corazón handout with information on healthier meals and increasing daily physical activity. In the remaining four learning sessions of Phase I, we will integrate previously tested and acceptable coping skills training sessions (i.e., goal-setting, problem-solving, cognitive restructuring, conflict resolution, assertiveness training) with a focus on barriers for perimenopausal Latinas. Trained bilingual CHWs will deliver learning sessions and 15-minute stress management sessions in groups of 20 participants.

Physical activity classes will be held for 45 minutes after the intensive intervention classes and will include a warm-up and then activities such as Zumba, Kick Boxing, walking, use of light weights and stretch bands, and a cool-down. A bilingual physical activity interventionist certified by the American College of Sports Medicine will teach the physical activity classes and reinforce ways to increase physical activity and decrease sedentary behaviors. At baseline, we will give participants an accelerometer and the RA will train them in its use as part of the intervention. The intervention group will be encouraged to increase their physical activity weekly by small increments until they are averaging 10,000 steps a day or 150 minutes per week; this group will also be provided information on the sociocultural and built environments such as a list of grocers where they can access healthy affordable food and free or low-cost spaces to exercise (e.g., YWCA/YMCA) close to home. Missed physical activity sessions will not be made up, but participants can make up learning and stress management sessions.

Continued Support

During Continued Support, participants will return to the church for classes once a month for 3 months. As a part of the intervention, participants engage in a discussion run by the bilingual CHW, who will help women solve problems they have encountered related to nutrition and physical activity for 60 minutes and then receive a 45 minute physical activity class and 15-minute stress management session. If a participant misses a class, the bilingual interventionist will call and ask how the woman doing and give the date of the next class. Continued support classes will not be made up.

Wait-List Control Group

Data will be collected from the wait-list control group at Time 1, Time 2, and Time 3; and participants will receive up to \$120 for their participations (\$35 at Time 1, \$40 at Time 2, and \$45 at Time 3) in addition to a \$5 transportation voucher at each data collection. The wait-list control group will receive a "thank you" postcard for their continued participation. Participants will receive a accelerometer and log book after they have completed Time 3 data. At that time, the wait-list control group (the cluster) will also be offered the intervention classes in the church. In addition the monthly "thank you" cards, participants will be called several days before classes and data collection to remind them.

